### 5.3 Major Events

Major Events are non-treatment-related grade 3 and 4 hematologic and non-hematologic toxicities. Treatment should be discontinued for major events if lapatinib may further complicate the non-treatment-related event. If a major event requires a delay of treatment, treatment must be delayed until toxicity is resolved ( $\leq$  grade 1 [or tolerable grade 2 for non-hematologic toxicity] or  $\leq$  baseline). If non-treatment-related toxicity is not resolved in  $\leq$

28 days, the patient will be removed from treatment. The ABTC Central Office should be consulted if it is not clear whether to continue or stop treatment.

#### 5.4 Use of Hematologic Growth Factors

No growth factors (G-CSF or GM-CSF) are to be used prophylactically in this protocol. Clinicians caring for patients on this protocol are permitted to use these growth factors to provide optimal care for patients with severe neutropenia in accordance with the ASCO 27 guidelines (JCO, 12, 1994: pp2471-2508). If these growth factors are used in the acute setting of neutropenia and infection (documented or suspected), they will not be utilized prophylactically in subsequent cycles and they will not subsequently be used in lieu of dose reduction of lapatinib.

#### 5.5 Toxicity Criteria

All toxicities will be described and graded according to the NCI Common Terminology Criteria for Adverse Events (CTCAE) version 5.0. All appropriate treatment areas should have access to a copy of the CTCAE version 5.0. A copy of the CTCAE version 5.0 can be downloaded from the CTEP web site ([http://ctep.cancer.gov/protocolDevelopment/electronic\\_applications/ctc.htm](http://ctep.cancer.gov/protocolDevelopment/electronic_applications/ctc.htm)). See also Section [9.2.4](#), Recording of Adverse Events.

### 6.0 PHARMACEUTICAL INFORMATION

#### 6.1 Lapatinib (GW572016, NSC 727989)

**Chemical Name:** N-{3-Chloro-4-[(3-fluorobenzyl)oxy]phenyl}-6-[5-({[2-(methylsulfonyl)ethyl]amino}methyl)-2 furyl]-4-quinazolinamine

**Other Names:** GW572016F, lapatinib ditosylate, Tykerb®

**Molecular Formula:** C29H26ClFN4O4S(C7H8O3S)2H2O

**Molecular Weight:** 943.48

**Approximate Solubility:** 0.007 mg/mL in water and 0.001 mg/mL in 0.1 N HCl at 25°C.

**Mode of Action:** Dual inhibitor of epidermal growth factor receptor (EGFR or ErbB1) and ErbB2 tyrosine kinases.

**How Supplied:** GlaxoSmithKline supplies and the NCI/DCTD distributes lapatinib as 250 mg oval, biconvex, orange film-coated tablets with one side plain and the opposite side debossed with FG HLS. The tablets contain 405 mg of lapatinib ditosylate

monohydrate, equivalent to 250 mg lapatinib free base per tablet. The tablets are packaged into HDPE bottles with child-resistant closures containing 90 tablets per container.

Excipients present in the tablet include: Microcrystalline cellulose, povidone, sodium starch glycolate, and magnesium stearate.

The film-coat contains: Hypromellose methylcellulose, titanium dioxide, macrogol/PEG 400, Polysorbate 80, FD&C Yellow No. 6, and FCF aluminum lake.

**Storage:** Store intact bottles at controlled room temperature (15°C-30°C).

**Stability:** Shelf life surveillance studies of the intact bottle are on-going.

**Route of Administration:** Oral on an empty stomach (either 1 hour before or 1 hour after meals).

**Method of Administration:** Whenever possible, administer whole tablets. Lapatinib tablets have not been deliberately formulated to be dispersible tablets; however, in circumstances where dosing of whole tablets is not possible, see procedure below. **Tablet crushing is not recommended.**

***For patients unable to swallow tablets, a suspension preparation in water or Kool-Aid can be made using the following procedure:***

1. Prepare Lemonade or Tropical Punch Kool-Aid as directed on package.
2. Place 2 or 4 ounces of water or Kool-Aid in a glass container, then add the required number of lapatinib tablets for dose (up to six tablets per 2 to 4 ounces) to the container.
3. Cover the container, let it stand for 5 minutes, and then stir the mixture intermittently for 15 minutes or until it is fully dispersed.
4. Stir the container for 5 seconds then administer.
5. Rinse the container with 2 ounces of water or Kool-Aid and repeat the administration process.

(The lemonade mixture appears somewhat like orange juice whereas the tropical punch mixture appears like carrot juice.)

**Potential Drug Interactions:** *In vitro* studies with human liver microsomes indicate that lapatinib is metabolized by CYP3A4 and CYP3A5, and to a lesser extent CYP2C19 and CYP2C8. Co-administration of lapatinib with potent or moderate CYP3A4 inhibitors (including grapefruit juice) and all CYP3A4 inducers is prohibited. Assess risk/benefit before co-administering lapatinib with weak CYP3A4 inhibitors. CYP3A4 inhibitors may decrease lapatinib metabolism (increasing levels); while CYP3A4 inducers may increase lapatinib metabolism (decreasing levels).

In human subjects, lapatinib inhibited CYP3A4 and CYP2C8 at clinically relevant concentrations. Avoid co-administration of lapatinib with drugs that are substrates of CYP3A4 or CYP2C8 and have narrow therapeutic windows.

**Pgp inhibitors:** the following drugs are in vivo substrates of the P-gp transporter and may not be administered to patients receiving lapatinib: aliskiren, ambrisentan, colchicine, dabigatran etexilate, digoxin, everolimus, fexofenadine, imatinib, lapatinib, maraviroc, nilotinib, posaconazole, ranolazine, saxagliptin, sirolimus, sitagliptin, talinolol, tolvaptan, topotecan; clinically significant interactions have been demonstrated for the following drugs: digoxin, loperamide, saquinovir, and ritonavir

For **Potential Risks of Lapatinib**, see Section [9.2.1](#), Comprehensive Adverse Events and Potential Risks list (CAEPR) for lapatinib.

### 6.1.1 Agent Ordering

Lapatinib may be requested by the Principal Investigator (or their authorized designees) at each participating institution. Pharmaceutical Management Branch (PMB) policy requires that the agent be shipped directly to the institution where the patient is to be treated. PMB does not permit the transfer of agents between institutions (unless prior approval from PMB is obtained). The CTEP-assigned protocol number must be used for ordering all CTEP-supplied investigational agents. The responsible investigator at each participating institution must be registered with CTEP, DCTD through an annual submission of FDA Form 1572 (Statement of Investigator), Curriculum Vitae, Supplemental Investigator Data Form (IDF), and Financial Disclosure Form (FDF). If there are several participating investigators at one institution, CTEP-supplied investigational agents for the study should be ordered under the name of one lead investigator at that institution.

Active CTEP-registered investigators and investigator-designated shipping designees and ordering designees can submit agent requests through the PMB Online Agent Order Processing (OAOP) application (<https://eapps-ctep.nci.nih.gov/OAOP/pages/login.jsp>). Access to OAOP requires the establishment of a CTEP Identity and Access Management (IAM) account (<https://eapps-ctep.nci.nih.gov/iam/>) and the maintenance of an “active” account status and a “current” password. For questions about drug orders, transfers, returns, or accountability, call [contact] Monday through Friday between 8:30 am and 4:30 pm (ET) or email [[contact]](mailto:[contact]) anytime.

### 6.1.2 Agent Accountability

The investigator, or a responsible party designated by the investigator, must maintain a careful record of the inventory and disposition of all agents received from DCTD using the NCI Drug Accountability Record Form. *See the NCI Investigator's Handbook on the CTEP web site for Procedures for Drug Accountability and Storage.*

## 7.0 REGISTRATION PROCEDURES / PATIENT ENROLLMENT

This study is supported by the NCI Cancer Trials Support Unit (CTSU) Regulatory Office and uses the Oncology Patient Enrollment Network (OPEN).

### 7.1 CTEP Registration

Food and Drug Administration (FDA) regulations and National Cancer Institute (NCI) policy require all individuals contributing to NCI-sponsored trials to register and to renew their registration annually. To register, all individuals must obtain a Cancer Therapy Evaluation Program (CTEP) Identity and Access Management (IAM) account (<https://ctepcore.nci.nih.gov/iam>). In addition, persons with a registration type of Investigator (IVR), Non-Physician Investigator (NPIVR), or Associate Plus (AP) (i.e., clinical site staff requiring write access to OPEN, RAVE, or TRIAD or acting as a primary site contact) must complete their annual registration using CTEP's web-based Registration and Credential Repository (RCR) (<https://ctepcore.nci.nih.gov/rcr>). Documentation requirements per registration type are outlined in the table below.

Documentation Required	IVR	NPIVR	AP	A
FDA Form 1572	✓	✓		
Financial Disclosure Form	✓	✓	✓	
NCI Biosketch (education, training, employment, license, and certification)	✓	✓	✓	
HSP/GCP training	✓	✓	✓	
Agent Shipment Form (if applicable)	✓			
CV (optional)	✓	✓	✓	

An active CTEP-IAM user account and appropriate RCR registration is required to access all CTEP and CTSU (Cancer Trials Support Unit) websites and applications. In addition, IVRs and NPIVRs must list all clinical practice sites and IRBs covering their practice sites on the FDA Form 1572 in RCR to allow the following:

- Added to a site roster
- Assigned the treating, credit, consenting, or drug shipment (IVR only) tasks in OPEN
- Act as the site-protocol PI on the IRB approval

- Assigned the Clinical Investigator (CI) role on the Delegation of Tasks Log (DTL).

Additional information can be found on the CTEP website at <https://ctep.cancer.gov>. For questions, please contact the RCR *Help Desk* by email at [[contact]](mailto:[contact]).

## 7.2 Site Registration

Each investigator or group of investigators at a clinical site must obtain IRB approval for this protocol and submit IRB approval and supporting documentation to the CTSU Regulatory Office before they can enroll patients. Assignment of site registration status in the CTSU Regulatory Support System (RSS) uses extensive data to make a determination of whether a site has fulfilled all regulatory criteria including but not limited to the following:

- An active Federal Wide Assurance (FWA) number
- An active roster affiliation with the ABTC
- A valid IRB approval
- Compliance with all protocol-specific requirements.

In addition, the site-protocol Principal Investigator (PI) must meet the following criteria:

- Active registration status
- The IRB number of the site IRB of record listed on their Form FDA 1572
- An active status on a participating roster at the registering site.

### **Downloading Site Registration Documents:**

See ABTC website ([www.abtconsortium.org](http://www.abtconsortium.org)).

### **Requirements for Site Registration:**

- IRB approval (local IRB documentation, an IRB-signed CTSU IRB Certification Form, Protocol of Human Subjects Assurance Identification/IRB Certification/Declaration of Exemption Form, or combination is accepted)

### **Submitting Regulatory Documents:**

Submit required forms and documents to the CTSU Regulatory Office via the Regulatory Submission Portal, where they will be entered and tracked in the CTSU RSS.

Regulatory Submission Portal: [www.ctsuo.org](http://www.ctsuo.org) (members' area) → Regulatory Tab  
→Regulatory Submission

Institutions with patients waiting that are unable to use the Portal should alert the CTSU Regulatory Office immediately at [name] in order to receive further instruction and support.

### **Checking Your Site's Registration Status:**

You can verify your site registration status on the members' section of the CTSU website.

- Go to <https://www.ctsuo.org> and log in to the members' area using your CTEP-IAM username and password
- Click on the Regulatory tab
- Click on the Site Registration tab
- Enter your 5-character CTEP Institution Code and click on Go

Note: The status given only reflects compliance with IRB documentation and institutional compliance with protocol-specific requirements outlined by the ABTC. It does not reflect compliance with protocol requirements for individuals participating on the protocol or the enrolling investigator's status with the NCI or their affiliated networks.

### **7.3 Patient Registration**

Patient enrollment will be facilitated using the Oncology Patient Enrollment Network (OPEN). OPEN is a web-based registration system available to users enrolling patients to ABTC studies from 9 a.m. to 4:30 p.m. Eastern Time. To access OPEN, the site user must have an active CTEP-IAM account (check at <https://ctepcore.nci.nih.gov/iam>) and a 'Registrar' role in ABTC. Registrars must hold a minimum of an AP registration type.

All site staff will use OPEN to enroll patients to this study. It is integrated with the CTSU Enterprise System for regulatory and roster data and, upon enrollment, initializes the patient in the Rave database. OPEN can be accessed at <https://open.ctsuo.org> or from the OPEN tab on the CTSU members' side of the website at <https://www.ctsuo.org>. To assign an IVR or NPIVR as the treating, crediting, consenting, drug shipment (IVR only), or investigator receiving a transfer in OPEN, the IVR or NPIVR must list on their Form FDA 1572 in RCR the IRB number used on the site's IRB approval.

Patient enrollment for this study will be facilitated using the Slot-Reservation System in conjunction with the Registration system in OPEN. Prior to discussing protocol entry with the patient, site staff must check the ABTC website ([www.abtconsortium.org](http://www.abtconsortium.org)) for protocol status and slot availability. Site staff must also use the CTSU OPEN Slot Reservation System to insure that a slot on the protocol is available to the patient. Once a slot-reservation confirmation is obtained, and the ABTC Central Office has notified the site of the randomization assignment, site staff may then proceed to enroll patients to this study.

Prior to accessing OPEN, site staff should verify the following:

- All eligibility criteria have been met within the protocol stated timeframes. Site staff should use the registration forms provided on the group web site as a tool to verify eligibility.

- All patients have signed an appropriate consent form and HIPAA authorization form (if applicable).

Access requirements for OPEN:

- Site staff will need to be registered with CTEP and have a valid and active CTEP-IAM account. This is the same account (user id and password) used for credentialing in the CTSU members' web site.
- To perform registrations, the site user must have been assigned the 'Registrar' role on the relevant Group or CTSU roster.

The OPEN system will provide the site with a printable confirmation of registration and treatment assignment information. Please print this confirmation for your records. Upon completion of the registration process in OPEN, sites must contact the ABTC Central Office to obtain confirmation of the patient's registration and treatment assignment.

Further instructional information is provided on the CTSU members' web site OPEN tab or within the OPEN URL (<https://open.ctsu.org>). For any additional questions contact the CTSU Help Desk at [name] or [[contact]](mailto:[contact]).

## **8.0 SAFETY AND QUALITY ASSURANCE**

### **8.1 Criteria for Response Assessment**

Subjects with measurable disease will be assessed by the RANO (radiographic assessment in neuro-oncology) criteria (Wen et al. 2010). For the purposes of this study, subjects should be re-evaluated at the end of every 2 cycles (approximately every 8 weeks) with a contrast-enhanced cranial MRI scan. The response will be determined as outlined in the RANO criteria below.

The MRI obtained prior to starting post-surgery treatment cycles of lapatinib will be used as the baseline MRI for purposes of determining radiographic response.

*Measurable disease.* Bidimensionally, contrast-enhancing, measurable lesions with clearly defined margins by MRI scan, with a minimal diameter of 1 cm, and visible on 2 axial slices which are at least 5 mm apart with 0 mm skip. Measurement of tumor around a cyst or surgical cavity, if necessary, requires a minimum thickness of 3 mm. If there are too many measurable lesions to measure at each evaluation, the investigator must choose the largest two to be followed before a participant is entered on study. The remaining lesions will be considered non-measurable for the purpose of objective response determination. Unless progression is observed, objective response can only be determined when all measurable and non-measurable lesions are assessed.

Complete Response (requires all of the following):

- a) Complete disappearance of all enhancing measurable and non-measurable disease sustained for at least 4 weeks. In the absence of a confirming scan 4 weeks later, this scan will be considered only stable disease.
- b) No new lesions.
- c) All measurable and non-measurable lesions must be assessed using the same techniques as baseline.
- d) Subjects must be off corticosteroids (or on physiologic replacement doses only).
- e) Stable or improved non-enhancing (T2/FLAIR) lesions.
- f) Stable or improved clinically.

**Note:** Subjects with non-measurable disease cannot have a complete response. The best response possible is stable disease.

Partial Response (requires all of the following):

- a) Greater than or equal to 50% decrease compared to baseline in the sum of products of perpendicular diameters of all measurable enhancing lesions sustained for at least 4 weeks. In the absence of a confirming scan 4 weeks later, this scan will be considered only stable disease.
- b) No progression of non-measurable disease.
- c) No new lesions.
- d) All measurable and non-measurable lesions must be assessed using the same techniques as baseline.
- e) The corticosteroid dose at the time of the scan evaluation should be no greater than the dose at time of baseline scan.
- f) Stable or improved non-enhancing (T2/FLAIR) lesions on same or lower dose of corticosteroids compared to baseline scan.
- g) Stable or improved clinically.

**Note:** Subjects with non-measurable disease cannot have a partial response. The best response possible is stable disease.

Stable Disease (requires all of the following):

- a) Does not qualify for CR, PR, or progression.
- b) The designation of stable disease requires a minimum of 4-week duration.
- c) All measurable and non-measurable sites must be assessed using the same techniques as baseline.
- d) Stable non-enhancing (T2/FLAIR) lesions on same or lower dose of corticosteroids compared to baseline scan. In the event that the corticosteroid dose was increased for new symptoms and signs without confirmation of disease progression on neuroimaging, and subsequent follow-up imaging shows that this increase in corticosteroids was required because of disease progression, the last scan considered to show stable disease will be the scan obtained when the corticosteroid dose was equivalent to the baseline dose.

e) Stable clinically.

Progressive Disease (defined by any of the following):

- a)  $\geq 25\%$  increase in sum of the products of perpendicular diameters of enhancing lesions compared to the smallest tumor measurement obtained either at baseline (if no decrease) or best response, on stable or increasing doses of corticosteroids.\*
- b) Significant increase in T2/FLAIR non-enhancing lesion on stable or increasing doses of corticosteroids compared to baseline scan or best response following initiation of therapy,\* not due to co-morbid events (radiation therapy, demyelination, ischemic injury, infection, seizures, postoperative changes, or other treatment effects).
- c) Any new lesion.
- d) Clear clinical deterioration not attributable to other causes apart from the tumor (e.g., seizures, medication adverse effects, complications of therapy, cerebrovascular events, infection, etc.) or changes in corticosteroid dose. The definition of clinical deterioration is left to the discretion of the treating physician, but it is recommended that a decrease in 20% of KPS or from any baseline to 50% or less be considered, unless attributable to comorbid events.
- e) Failure to return for evaluation due to death or deteriorating condition.
- f) Clear progression of non-measurable disease.

\* Stable doses of corticosteroids include patients not on corticosteroids.

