#### 3.2 Eligibility Criteria

1. Patients must have histologically proven WHO grade IV glioblastoma/ gliosarcoma or WHO grade III glioma (anaplastic astrocytoma, anaplastic oligodendroglioma, mixed anaplastic oligoastrocytoma, anaplastic ependymoma) which is progressive or recurrent following radiation therapy ± chemotherapy.

2. Patients must have measurable, supratentorial contrast-enhancing progressive or recurrent high-grade glioma by MRI imaging within 21 days of starting treatment. Patient must be able to tolerate MRIs.
3. Patients may have an unlimited number of prior therapy regimens.
4. Patients must have recovered from severe toxicity of prior therapy. The following intervals from previous treatments are required to be eligible:
  - 12 weeks from the completion of radiation
  - 6 weeks from a nitrosourea chemotherapy
  - 3 weeks from a non-nitrosourea chemotherapy
  - 4 weeks from any investigational (not FDA-approved) agents
  - 4 weeks from the last treatment with bevacizumab
  - 2 weeks from administration of a non-cytotoxic, FDA-approved agent other than bevacizumab (e.g., hydroxychloroquine, etc.)
5. Patients must be undergoing surgery that is clinically indicated as determined by their care providers. Patients must be eligible for surgical resection according to the following criteria:
  - Expectation that the surgeon is able to resect at least 500 mg of tumor from enhancing tumor and 100 mg from non-enhancing tumor with low risk of inducing neurological injury.
6. Patient tumor sample must have evidence of EGFR gene amplification by FISH performed using a CLIA-certified laboratory assay. See Section [9.5.2](#) for details.
7. Paraffin embedded tissue must be available from initial surgical resection at diagnosis (prior to any treatment).
8. Patients must be 18 years of age or older.
9. Patients must have a Karnofsky Performance Status  $\geq 60\%$  (i.e. the patient must be able to care for himself/herself with occasional help from others).
10. Patients must have the following organ and marrow function:

Absolute neutrophil count	$\geq 1,500/\text{mcL}$
Platelets	$\geq 100,000/\text{mcL}$
Hemoglobin	$\geq 9 \text{ g/dL}$
Total bilirubin	$\leq$ institutional upper limit of normal
AST (SGOT)/ALT (SGPT)	$\leq 3 \times$ institutional upper limit of normal
Creatinine	$\leq$ institutional upper limit of normal

OR

Creatinine clearance  $\geq 60$  ml/min/1.73m^2 for patients with creatinine levels above institutional normal  

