### 4.1 Treatment Schema

All patients must have recurrent EGFR-amplified high-grade glioma and be candidates for re-resection.

[figure not shown]
The first 8 patients on the study will be enrolled into Group A and receive lapatinib pre-operatively for 4 doses. Intratumoral drug levels will be analyzed following tissue sample collection during surgery. If adequate intratumoral drug concentration levels (1.5  $\mu$ M or higher) are reached in at least 3 of the initial 8 patients, the study will proceed with further enrollment as follows. See Section [11.0](#), Primary Objectives and Sample Size for details.

After the initial 8 patients are enrolled, subsequent patients will be sequentially assigned to either receive lapatinib pre-operatively for 4 doses (Group A) or to receive no drug prior to surgical resection ([Reference Group](#)): 20 patients will alternate enrollment into either Group A or the Reference Group (10 additional patients into Group A to complete the group, and 10 patients into the Reference Group); then 5 additional patients will enroll into the Reference Group to complete the group. Fresh and paraffin embedded tissue from surgical resection will be utilized for correlative studies.

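### When lesions are too numerous to measure, Section 8.1 fixes the two to be followed before study entry, hence before the protocol resection, yet scores response from the post-surgery MRI

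*Combined protocol and SAP*

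**What the plan says.** Four parts of the combined protocol and SAP bear on this.

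- **Choosing lesions (Section 8.1, measurable disease).** The rule is conditional: "If there are too many measurable lesions to measure at each evaluation", then "the investigator must choose the largest two to be followed before a participant is entered on study". For the others: "The remaining lesions will be considered non-measurable for the purpose of objective response determination".
- **Baseline (Section 8.1).** "The MRI obtained prior to starting post-surgery treatment cycles of lapatinib will be used as the baseline MRI for purposes of determining radiographic response".
- **Order of entry and surgery (Sections 3.2 and 4.1).** For the start of Group A: "The first 8 patients on the study will be enrolled into Group A and receive lapatinib pre-operatively for 4 doses". Later patients are assigned either to the same pre-operative course or "to receive no drug prior to surgical resection". Eligibility criterion 5 requires, of every patient, "Expectation that the surgeon is able to resect at least 500 mg of tumor from enhancing tumor".
- **Scoring (Sections 8.1 and 11.0).** A partial response needs a decrease of at least 50% from baseline in the summed products of the measurable enhancing lesions. Notes under complete and partial response limit subjects with non-measurable disease to stable disease. Section 11.0 reports the proportion with a complete or partial response, with an exact binomial 95% confidence interval.

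**The concern.** In a trial without surgery, naming the followed lesions at entry and measuring them at baseline would use the same picture of the disease. Here an operation on enhancing tumour falls between the two. The lesions are named on a pre-operative scan, and change is then measured from a post-operative one.

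Where the two-lesion rule is triggered and the operation removes a chosen lesion, the followed list no longer describes the disease present when post-surgery treatment starts. A residual lesion large enough to be measured is left out of the sum because of a choice made before surgery. If both chosen lesions are gone, nothing on the list can shrink, and the patient cannot be scored a responder whatever happens to the remaining tumour.

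At stake is the objective response rate, which Section 11.0 presents as evidence of biological activity, and the measured part of the progression criterion. A protocol-compliant site and a site that sensibly chooses again after surgery would score the same patient differently.

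**Working it through.** The plan states no figure that depends on this rule, so there is none to reproduce. The check is of timing, followed by constructed records.

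**1. Timing**

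| Step | When | Source |
|---|---|---|
| Eligibility MRI | Within 21 days before treatment starts | Sections 3.2, 4.2 |
| Two largest lesions chosen, if too many to measure | Before entry | Section 8.1 |
| Entry and group assignment | Before surgery | Sections 4.1, 7.3 |
| Resection of enhancing tumour | After entry | Sections 3.2, 4.1 |
| Post-operative MRI | 1-3 days after surgery; a new scan if the last is more than 21 days old at Cycle 1 | Section 9.1 footnotes |
| Response baseline | The MRI before the post-surgery cycles | Section 8.1 |

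Sections 8.1, 8.2, 9.1 and 11.0 contain no rule for choosing lesions again on the post-operative scan.

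**2. Constructed records.** These lesion sizes are assumptions, not trial data, and both records are conditional on three lesions being judged too many to measure. Before entry: A 4 x 4 = 16 cm², B 2 x 2 = 4 cm², C 1.5 x 1.5 = 2.25 cm². A and B are followed; C is non-measurable by rule although it exceeds the 1 cm minimum diameter.

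*Only A is removed.* B later falls from 4.0 to 1.8 cm² and C stays at 2.25 cm².

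- By the rule, B alone: (1.8 - 4.0)/4.0 = -55%, which meets the 50% threshold.
- With lesions chosen at the response baseline, B + C: 4.0 + 2.25 = 6.25 falls to 1.8 + 2.25 = 4.05, and (4.05 - 6.25)/6.25 = -35.2%, which does not.

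This reads the note under partial response as covering subjects who have only non-measurable disease, which fits item b of the same definition, since that item allows such disease to be present. If the note covers anyone with any non-measurable disease, the rule instead caps this patient at stable disease because C was left off the list. Under either reading, the pre-entry list decides the score.

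*A and B are both removed.*

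- By the rule, the followed sum at baseline is 0 and C is non-measurable, so stable disease is the best possible score. A percentage change from 0 is also undefined, for the 50% decrease and for the 25% increase alike. Progression could still be called through other criteria in Section 8.1, such as a new lesion or clear progression of non-measurable disease.
- With lesions chosen at the response baseline, C (2.25 cm²) is followed and can respond.

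The error can therefore run in either direction.

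**3. Weight of one patient.** Section 3.1 plans 18 + 15 = 33 patients. One misclassified patient moves the response rate by 1/33 = 3.0 percentage points, and by more if fewer are evaluable. For scale, 3/33 = 9.1% has an exact 95% interval of 1.9% to 24.3%, and 4/33 = 12.1% has 3.4% to 28.2%.

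**The case against.** The best defence has four parts.

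- **The trigger is narrow.** The choice is forced only when lesions are too many to measure, and no number is set. A reader might infer that anyone with more than two measurable lesions is affected; the text does not say so. If three lesions can all be measured, none is relabelled and both constructed records fall away. This stands, and it limits the reach of the point.
- **The baseline sentence is specific to this trial.** The entry clause looks like general wording, and a sensible site would measure on the stated baseline. That is plausible, but the clause is mandatory and names a time. A site that chooses again departs from it, and a site that complies may be following lesions that no longer exist.
- **Central review.** Sections 8.2 and 8.4 send scans showing response to a neuroradiologist who assesses size independently. A reader might infer that this reading inherits the site's list; nothing in the documents binds it to that list. A site-called response such as the 55% case would be checked. A missed response would not, because only scans showing response are reviewed.
- **Little is at stake.** A missed response needs the rule to be triggered, both chosen lesions removed, another measurable lesion left, and that lesion to respond. Eligibility expects 500 mg of enhancing tissue, not removal of two separate lesions. Assuming 5-15% of patients trigger the rule, 10-50% of those lose both lesions, and 5-20% would truly respond, the expected number of missed responses in 33 runs from 33 x 0.05 x 0.10 x 0.05 = 0.01 to 33 x 0.15 x 0.50 x 0.20 = 0.5. None of these rates is in the documents, and the sum leaves out the partial-resection route. It does support the view that the numbers are small.

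**Conclusion.** The point holds in a limited form. Where the two-lesion rule is triggered, Section 8.1 fixes the followed lesions on a scan that is not the response baseline, with the protocol resection in between, and no other section corrects this. It is a rule that gives the wrong list if followed, rather than an omitted detail.

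The affected patients are those in whom lesions are judged too many to measure and a chosen lesion is resected. The documents do not allow them to be counted. A reader might take an assumed 5-15% of patients with several lesions, about 2 to 5 of 33, as the number affected. The documents support neither the percentage nor that step, since some of those patients would keep their chosen lesions.

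The effect is confined to the secondary/exploratory response rate and to progression measured on the same lesions. The response rate is an estimate with no test or decision rule attached, and one patient's shift of 3.0 points is small beside its interval. The primary tumour-concentration and EGFR-phosphorylation endpoints are untouched. The case for changing the text rests on the rule being wrong as written and the repair being nearly free, not on a large expected bias.

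**What to change.** In the measurable-disease paragraph of Section 8.1, keep the opening condition and change only when the choice is made: the investigator must choose the largest two lesions on the post-surgery, pre-Cycle 1 MRI (the response baseline), before the first post-surgery dose of lapatinib. Keep the pre-entry MRI for eligibility only.

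The cost is one sentence of protocol wording. Section 4.2 already requires a post-surgical MRI within 21 days before Cycle 1, so no scan, visit or reader is added.
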